Study Protocol:

Systemic Lupus Erythematosus and Heart Conduction Disorders

NCT number: 02162992

Latest version: Feb 22nd, 2016

BACKGROUND

The incidence of sudden death and cardiac rhythm disorders is higher in patients with autoimmune diseases than in the general population.¹ Congenital atrioventricular block (AVB) in neonates has been classically associated with the transplacental passage of maternal anti-Ro antibodies.²

Complete AVB in adult patients with connective diseases is extremely rare, although not absent. From 1986 to 2015, 21 cases have been described in the medical literature of complete AVB in patients with connective diseases, 42% of whom were patients diagnosed with systemic lupus erythematosus. Of the total, 76% were positive for anti-Ro / SSA.1 antibodies, (PubMed® 1989-2015, keywords: atrioventricular block, autoimmune disease, systemic lupus erythematosus, SSA / anti-Ro antibodies).

Anti-Ro antibodies can be positive in several systemic diseases such as systemic lupus erythematosus, Sjögren's syndrome, polymyositis, dermatomyositis, systemic sclerosis and in 3% of the general population.¹ The pathogenesis of conductive defects in connective diseases in adults has been classically associated with infiltration of the conduction tissue by fibrosis or granulation tissue in some cases, with occlusion of the artery of the atrioventricular nodule by vasculitis in others, and with sequelae of myocarditis in others.^{1,3,4}

The pathogenesis of cardiac conduction disorders in patients positive for anti-Ro / SSA antibodies is not clearly elucidated and there are conflicting data in this regard.^{3,4} Recent experimental studies have allowed to elaborate a new theory in which there would be a unique pathogenic sequence based on the interaction of anti-Ro/SSA antibodies with the calcium channels of the cardiomyocyte surface. Anti-Ro antibodies would interact with calcium channels by molecular mimicry causing reversible inhibition of calcium currents at first and, at a later stage, internalization of these channels which would induce apoptosis and cell death. This would lead to a process of local inflammation that would sustainably create fibrosis of the conductive tissue. A possible explanation of the infrequent involvement of the adult heart compared to the neonate would be the greater dependence of the transsarcolemmic calcium passage, through L-calcium channels, due to the underdevelopment of the neonatal sarcoplasmic reticulum.^{1,5}

In June 2013, our group described the first case of complete BAV in a young patient with anti-Ro/SSA positive antibodies in whom an electrophysiological study is available and therefore the level of conduction block could be located, being this distal to the atrio-ventricular node. Together

with the presence of the left bundle branch block, these data suggested a specific involvement of Purkinje fibers.⁶

The only information available on this subject is based on isolated cases like ours. There are no publications on the subsequent follow-up of these patients, nor recommendations on the therapeutic attitude or cardiologic check-up in patients with connective diseases and anti-Ro/SSA antibodies. And there is not established indication for anti-Ro/SSA antibodies testing in young patients without known autoimmune pathology who have been diagnosed with an AVB.

Therefore, we carried out a first retrospective observational study in which the data of all patients implanted with a pacemaker in our center from 1987 to 2011 were reviewed. The study group included young adults between 18 and 50 years of age at the time of pacemaker implantation due to AVB of unknown origin and without structural heart disease. A total of 19 patients, with a mean implant age of 36 ± 10 years, was studied with clinical evaluation and an immunological study including antinuclear antibodies (ANA), extractable nuclear antigens (ENA) and anti-Ro/SSA. Six patients (31.6%) presented markers of immune disease, of whom 2 patients (10.5%) showed antibodies against specificities SS-A / Ro.¹⁴

The next step is to conduct a prospective analysis study of adult patients with autoimmune disease and presence of anti-SS-A/Ro antibodies and compare them with negative anti-SS-A/Ro patients to determine the existence of conduction disorders or other disorders by electrocardiographic non-invasive methods.

- To determine if the positivity for subunit 60 of the Ro autoantibody is associated with cardiac conduction disorders or alteration of cardiac repolarization by lengthening the QT interval.

METHODOLOGY

Design

- It is a cross-sectional study of which an observational analysis will be carried out.

Subjects

- Target population: Patients with SLE visited in the Rheumatology service of an hospital in Catalonia.
- Accessible population: Patients with SLE visited in the Rheumatology service of the Germans Trias i Pujol University Hospital in Badalona.

Criteria for selecting subjects:

- Inclusion criteria:
 - Diagnosis of SLE according to the 1997 diagnostic criteria (see annex 2).
- Exclusion criteria:
 - Presence of cardiac structural disease:
 - Ischemic heart disease
 - Congenital or acquired structural heart disease (hypertrophic cardiomyopathy, idiopathic dilated cardiomyopathy, valvular heart disease).
 - History of cardiac surgery or cardiac ablation procedures.
 - History of other pathological processes that could affect cardiac conduction:
 - Steinert's disease
 - Lyme disease
 - Chagas disease
 - Hypothyroidism

Recruitment

The selection of patients and controls will be carried out by a consecutive sampling of the patients visited in the Rheumatology office.

MEASUREMENTS

Main variables:

- Study of cardiac conduction disorders by analyzing the resting electrocardiogram and 24-hour Holter.

Descriptive variables:

- Collection of the general pathological history of the patients, with targeted interrogation of the rheumatic and cardiac involvement and registration of the usual medication.
- Weight and height and physical examination.
- ECG at rest: analysis of the base rhythm, PR duration, QRS and QT intervals. Presence of intraventricular conduction disorders. Presence of ectopic beats.
- 24-hour Holter recordings: presence and number of ventricular ectopic beats, classification of episodes according to Lown's criteria. Presence of significant pauses (RR intervals > 2000 msec). QTc interval measurement. Autonomic dysfunction parameters: time domain parameters, such as the average of the RR intervals, the standard deviation of all normal RR intervals (SDNN), the root of the difference of successive means between the normal adjacent RR intervals (RMSSD), and the percentage of adjacent intervals with more than 50 ms (PNN50).
- Basic transthoracic echocardiogram: with analysis of ventricular diameters, systolic and diastolic function, valvular morphology and functionalism, determination of systolic pulmonary pressure, study of pericardial involvement and screening of acquired or congenital structural heart disease.
- Serological analysis: immunological profile, organic involvement by lupus, activity indices and chronic lupus damage. (see annex 3)

Confusion factors:

- Concomitant medication with effect on AV conduction function.
- Immune profile.

STATISTICAL PLAN

With the hypothesis of demonstrating a correlation greater than 0.5 or greater difference in the control to 20%, a sample size has been calculated around 57 patients and 29 controls (for statistical power of 0.8, confidence interval and a ratio of 0.95 cases / controls 0.5). Since the aim of the study was to perform an analysis adjusted for confounders, and there are at least four factors (taking concomitant medication with effect on AV conduction, advanced age, sex and immunological profile) it has decided to predetermine the sample size of 100 cases and 50 controls.

First there will be a description of the sample, obtaining the average and standard deviation positive and negative for each of the variables in the group of 52 Ro-positive and the negative Ro52 as well as the percentage of the same. We will calculate the differences concerning the distribution of variables between groups using the Student t test and chi square. The analysis of association between these variables is made by linear regression analysis in the presence or absence of other factors, from which it obtained the odds ratio (odds ratio

- The obtained variables will be compared using Student's t-test for quantitative data and Fisher's and chi-square tests for qualitative data.
- Pearson correlation coefficient will be used to analyze the correlation between two variables.
- Calculations will be made using SPSS statistics software.
- The significance level adopted will be 5%.

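### Does the 57/29 sample-size calculation fail because it gives no control rate and prints the case/control ratio the wrong way round?

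*Combined protocol and SAP*

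**What the plan says.** The sample-size paragraph of the Statistical Plan sets the target as "demonstrating a correlation greater than 0.5 or greater difference in the control to 20" per cent. From this, "a sample size has been calculated around 57 patients and 29 controls (for statistical power of 0.8"), a 0.95 confidence level and "a ratio of 0.95 cases / controls 0.5". It then allows for adjustment for at least four factors (medication acting on AV conduction, age, sex and immunological profile) by choosing to "predetermine the sample size of 100 cases and 50 controls".

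The same section sets significance at 5% and names Fisher's "and chi-square tests for qualitative data". The paragraph does not name the outcome, label a rate for either group, or give the sidedness or the formula. The outcome can be inferred from elsewhere: the first item under Hypothesis is a higher frequency of conduction disorders in Ro-positive patients, and Measurements lists conduction disorders on ECG and Holter as the main variable.

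**The concern.** A 20% difference and a power of 0.8 do not fix a sample size for two proportions, because the control rate is also needed. If 20% means 20 percentage points, 57/29 reaches 80% power only at a very low control rate (or at a mirror-image rate of about 77% or more, which seems implausible here), and the plan states neither. At a 10% control rate the exact chi-square power of 57/29 would be 58%. The adopted 100/50 would keep 80% only up to a control rate of about 11-12%.

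Two further things add to the doubt. The printed cases/controls ratio of 0.5 contradicts both pairs of group sizes. The increase to 150 patients is credited to adjustment, with no allowance or resulting power shown. The background calls the existing data on the antibodies' effect on adult cardiac tissue controversial, so a null result is possible. How to read it would depend on the effect the study could detect.

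**Working it through.** **Inputs, all from the Statistical Plan:** the numbers 0.5 and 20%; power 0.80; confidence 0.95, so alpha 0.05 (two-sided assumed); groups of 57 and 29, then 100 and 50. The normal quantiles sum to 1.960 + 0.842 = 2.802.

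**1. The ratio.** 57/29 = 1.97 and 100/50 = 2.00 cases per control. Inverted, 29/57 = 0.51 and 50/100 = 0.50. The printed 0.5 is controls/cases with the label reversed.

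**2. Reproducing 57/29, with 0.5 and 20% as case and control proportions.** Arcsine formula with k = 2 cases per control:

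- h = 2·arcsin(√0.5) − 2·arcsin(√0.2) = 1.5708 − 0.9273 = 0.6435
- controls = (1 + 1/k)·(2.802/h)² = 1.5 × 18.95 = 28.43, rounded up to **29**
- cases = 2 × 28.43 = 56.86, rounded up to **57**

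The pooled formula gives controls = [1.960·√(0.4·0.6·1.5) + 0.842·√(0.2·0.8 + 0.5·0.5/2)]² / 0.30² = 29.35, that is 30 controls and 59 cases, within two patients of the plan's figures.

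**3. Reading the labels literally.**

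- A correlation of 0.5 by Fisher's z needs n = (2.802/0.5493)² + 3 = 29.0 patients in total. This happens to equal the number of controls but does not explain 57 cases.
- For a 20-point difference, the arcsine formula gives exactly 57/29 at no control rate on a 1% grid. The highest low-end control rate at which 57/29 has 80% power is 0.5% (pooled), 0.95% (exact Fisher), 2.5% (exact chi-square), 3.4% (arcsine) or 5.4% (unpooled).

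**4. Exact power of the two named tests, unadjusted, two-sided 5%, by enumerating both binomials:**

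| Groups | Cases vs controls | Chi-square | Fisher |
|---|---|---|---|
| 57/29 | 50% vs 20% | 79.6% | 73.2% |
| 57/29 | 22.5% vs 2.5% | 80.1% | 68.9% |
| 57/29 | 30% vs 10% | 58.1% | 51.8% |
| 100/50 | 50% vs 20% | 96.2% | 95.4% |
| 100/50 | 30% vs 10% | 83.3% | 81.4% |
| 100/50 | 32% vs 12% | 80.3% | 77.9% |
| 100/50 | 40% vs 20% | 71.3% | 68.4% |

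**5. The increase.** From 57 + 29 = 86 to 100 + 50 = 150 is a rise of 64/86 = 74%. No inflation formula is given, but a margin was clearly added.

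**The case for a change.** The strongest case for acting is that the plan calls 0.5 a correlation and 20% a difference, so the match at 50% against 20% requires relabelling both. It could also be a coincidence. On a 5% grid of rate pairs, three others also give exactly 57/29 by arcsine: 0% and 10%, 50% and 80%, 90% and 100%. The two readings differ in what they say about 100/50. Power is about 96% for 50% against 20%, but 71% by chi-square for 40% against 20%. Even on the favourable reading, Fisher's test at 57/29 has 73% power rather than 80%.

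Much of this stands as a remark on clarity. The paragraph does not say which effect was used, and the documents do not confirm the 50%-against-20% reading. It does not establish an error. Among the four matching pairs, only 20% and 50% uses both printed numbers, and it needs no unstated rate, whereas the 20-point reading needs one that appears nowhere. The Fisher shortfall applies to 57/29, which the study did not adopt; at 100/50 the same contrast has 95% power by Fisher. The 11-12% limit holds only if 20% was meant as an absolute difference.

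**Conclusion.** The concern does not hold as an arithmetic error. The printed numbers reproduce 57/29 exactly if they are 50% in cases and 20% in controls, with the arcsine formula, two-sided 5%, power 0.8 and two cases per control. The adopted 100/50 then has about 96% exact chi-square power before adjustment. Confidence in that reading is moderate, since it is inferred from a garbled sentence. On the other reading, a 20-point absolute difference, 100/50 still has 80% unadjusted power by chi-square up to a control rate of about 12% (10.8% by Fisher). Power after adjustment cannot be derived from the documents on either reading.

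What remains is a reversed ratio label, which 57/29 and 100/50 already resolve, and unlabelled assumptions: the two rates, the outcome, the sidedness, the formula and the adjustment allowance. The first is clerical. The others are missing detail in the justification of a size that is already fixed, in a cross-sectional observational study. Supplying them would move no patient, test or estimate. When results are read, the confidence interval for the difference will show what a null finding can exclude, whichever planning effect was used.

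### If the Ro52 groups end up near 2:1, naming Student's t-test leaves the QT and PR comparisons sensitive to unequal spread; Welch's test is a near-free safeguard (low severity).

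*Combined protocol and SAP*

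**What the plan says.** The Statistical Plan names the test twice. The groups, described as "in the group of 52 Ro-positive and the negative Ro52", are to be compared "using the Student t test and chi square". The list that closes the section repeats it: "The obtained variables will be compared using Student's t-test for quantitative data". The significance level is 5% and the software is SPSS.

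For size, the plan reports that "a sample size has been calculated around 57 patients and 29 controls", and then decides, to allow for confounder adjustment, to "predetermine the sample size of 100 cases and 50 controls".

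The plan names no unequal-variance version of the test, no check of equal variances and no alternative for skewed variables. It gives no SD for any variable. It does not say that the cases are the Ro52-positive patients. Under Recruitment, selection "will be carried out by a consecutive sampling of the patients visited in the Rheumatology office", with no quota by Ro status.

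**The concern.** Student's t-test pools the two variances. With equal groups, unequal SDs hardly matter. With a 2:1 split, the larger group dominates the pooled variance, so the standard error of the difference is wrong whenever the SDs differ. It is too large if the smaller group is the less variable one, and too small if it is the more variable one.

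Unequal spread is plausible under the study's own hypothesis. If anti-Ro antibodies prolong PR or QT in only some carriers, the positives are a mixture of affected and unaffected patients and have a larger SD than the negatives. QT lengthening is one of the stated objectives and is not listed under Secondary Objectives. At stake are the power of that comparison, or its false-positive rate, and the width of its confidence interval.

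**Working it through.** **The plan's own figure.** The 57 and 29 cannot be reproduced from the stated inputs alone, because no control rate is given. The nearest match comes from the two-sided two-proportion formula without continuity correction, with 0% in controls and 20% in cases. The average rate at 2:1 is 0.4/3 = 0.1333. Controls = [1.96 × √(1.5 × 0.1333 × 0.8667) + 0.8416 × √(0.2 × 0.8/2)]² / 0.2² = (0.816 + 0.238)²/0.04 = 27.8, so 28 controls and 56 cases. Nothing below depends on this figure.

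**Inputs.**
- From the Statistical Plan: Student's t-test, a 5% level, targets of 100 and 50.
- Assumed: a two-sided test, normal data, Ro52 groups of 100 and 50, and an SD ratio r (group of 50 over group of 100) between 0.5 and 2.

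**Type I error, large-sample formula.** Set the SD of the group of 100 to 1.
- Expected pooled variance: (99 + 49r²)/148.
- Variance that Student's test assigns to the difference: A = pooled variance × (1/100 + 1/50).
- True variance of the difference: B = 1/100 + r²/50.
- Type I error ≈ 2 × [1 − Φ(1.96 × √(A/B))].

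For r = 2: pooled variance 295/148 = 1.993, A = 0.0598, B = 0.0900, √(A/B) = 0.815, critical value in effect 1.598, error 11.0%.

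For r = 0.5: pooled variance 111.25/148 = 0.752, A = 0.02255, B = 0.0150, √(A/B) = 1.226, critical value in effect 2.403, error 1.6%.

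Simulation (400,000 runs per setting) agrees:

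| r | Student, formula | Student, simulated |
|---|---|---|
| 0.5 | 1.6% | 1.7% |
| 0.67 | 2.6% | 2.6% |
| 0.8 | 3.5% | 3.5% |
| 0.9 | 4.2% | 4.3% |
| 1 | 5.0% | 5.0% |
| 1.1 | 5.8% | 5.7% |
| 1.25 | 6.9% | 6.8% |
| 1.5 | 8.5% | 8.4% |
| 2 | 11.0% | 11.1% |

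Welch's test stays between 4.95% and 5.07% throughout. At 75/75, A equals B for every r and Student's test simulates at 5.0% to 5.1%, so the problem needs the unequal split.

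**What the study's own mechanism implies.** Assume 20% of positives are shifted upward by d, in SDs of unaffected patients. The positives' SD is then √(1 + 0.2 × 0.8 × d²) and the mean difference is 0.2d. With the positives as the 100, simulated power is:

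| d | SD, positives over negatives | Student | Welch |
|---|---|---|---|
| 1 | 1.08 | 19% | 20% |
| 1.5 | 1.17 | 33% | 37% |
| 2 | 1.28 | 48% | 55% |
| 2.5 | 1.41 | 62% | 70% |
| 3 | 1.56 | 72% | 81% |

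The loss is about 1 to 9 points. If the positives are the 50, the same ratios put the extra spread in the smaller group (r = 1.08 to 1.56). The type I error table then applies on its liberal side, up to a little over the 8.4% at r = 1.5.

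**Cost of Welch's test.** With equal SDs at 100/50, the largest power difference over true differences of 0.2 to 0.6 SD is 0.3 points (63.2% against 62.9% at 0.4 SD).

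**Skewed data.** At r = 2, Student's and Welch's tests give 11.3% and 6.1% for exponential data, and 11.7% and 8.0% for lognormal data. Welch's test improves matters but does not fully restore 5%.

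**The case against.** The strongest reply is that the premises are not in the documents. No SDs are given. The 100/50 split is described as cases and controls, while the test compares Ro52 groups, and consecutive sampling may produce a different split. Student's test is not explicitly called pooled, and SPSS prints the unequal-variance row beside the pooled one. The presence of a conduction disorder is categorical and goes to the chi-square or Fisher test. The plan also intends a confounder-adjusted regression, so the t-test is only the unadjusted comparison.

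Most of this stands and limits the point. It makes the size unknown and the severity low. It does not remove the reason to change the test: Welch's version needs no knowledge of the split or of which group is more variable. Ordinary linear regression does not cure the problem either, since it also assumes constant variance.

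A reader might infer that the plan will produce false positives near 11%. The documents do not support that. Such a rate needs the smaller group to have twice the SD with equal means. If antibody status is unrelated to the variable, both groups share one distribution and Student's test holds 5%. If the positives are the 100 and the more variable group, the test is conservative, not liberal. A reader might also infer that Welch's test is a complete and free cure. It costs up to 0.3 power points when SDs are equal, and it falls short for strongly skewed variables.

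**Conclusion.** The point holds as a cheap improvement of low severity. If the Ro52 groups are near 2:1 and their SDs differ, Student's test departs from 5%: little at a 10% SD difference, and noticeably from a ratio of about 0.8 or 1.25 outward. The direction depends on which Ro52 group is the smaller, which the plan leaves open. If the positives are the larger group, expect lost power; if they are the smaller, expect a liberal test and a confidence interval that is too narrow. All sizes rest on assumed SD ratios, an assumed 20% affected fraction, normal data within patient groups, and a two-sided test. No error in the trial's results is shown.

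**What to change.** In the Statistical Plan, name Welch's unequal-variance t-test, with its confidence interval for the mean difference, as the reported result for PR, QRS, QT/QTc, mean RR and SDNN. Use heteroscedasticity-consistent standard errors in the linear regressions for the same variables. State which Ro52 group is meant to be the 100 and which the 50, or that the split is left to consecutive sampling. For ectopic beat counts, RMSSD and PNN50, prespecify a suitable transformation or a method for skewed data, because Welch's test alone may not suffice.

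The change is a few lines of text. It needs no extra patients or measurements, and the named software already prints the Welch row. Fixing the choice in advance also prevents picking between the two rows once results are seen.
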